associations between postnatal maternal depression and HEU cognitive and executive function^{35,36}. A recent study from Sweden which assessed over 500,000 sibling pairs found that higher birthweight was associated with significantly lower risk of depression, PTSD, ADHD, anxiety and ASD, after controlling for familial confounders³⁷. There is consistent evidence of lower birthweight and poorer growth in HEU compared to HUU^{38,39}. A recent study from Denmark with 485 HEU and 2,495 HUU observed significant growth differences between the groups at birth but differences decreased by 5 years of age⁴⁰. Growth trajectories in HEU may be less compromised among those who receive Option B+ vs. earlier or no PMTCT regimens, and may transition from underweight to overweight during infancy^{41,42, 43}. Using a fetal origins perspective, it is plausible that HEU may have poorer neurodevelopmental and mental health outcomes via fetal exposure to HIV, ART, poor fetal growth, or maternal stress or depression in pregnancy.

Option B+ PMTCT regimen switch from EFZ to DTG may influence HEU outcomes

In 2019, guidelines for ART changed from EFZ-backbone to DTG-backbone regimens, including during pregnancy. Psychiatric symptoms including insomnia, anxiety, depression and suicidality occur with both EFZ and DTG, generally at low prevalence with infrequent discontinuation; since these psychiatric symptoms are markedly increased with HIV infection it is difficult to attribute drug-effects⁴⁴. EFZ was associated with increased suicidal ideation at 12 months postpartum in a cohort of South African women⁴⁵. There is additional evidence that EFZ is associated with mild-moderate neurocognitive impairment, although mechanisms are unclear⁴⁶. Discontinuing EFZ improved sleep quality in a recent randomized trial⁴⁷. DTG administration in pregnancy results in high fetal exposure⁴⁸ and periconceptional DTG was associated with a slightly increased risk of neural tube defects in a large study of 119,033 infants in Botswana⁴⁹⁻⁵¹. In a US multi-site study of 3,747 HEU in the SMART (Surveillance Monitoring for ART Toxicity) cohort, fetal EFZ exposure was associated with increased neurologic conditions (microcephaly, seizures, and eye abnormalities) (Crowell *IDWeek* 2018). There have not been studies to determine long-term outcomes of EFZ and DTG on HEU neuropsychiatric outcomes.

Increased mortality and morbidity in HEU suggest impact of fetal HIV/ART exposure in diverse domains

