Kenyatta National Hospital & University of Nairobi: Study participants for aim 1 will be recruited, and followed up clinics in Nairobi and Western Kenya. Cross-sectional surveys (Aim 2) will be done in various sites across the country. Kenyatta National Hospital and University of Nairobi collaborators will participate in study design, data analysis and interpretation, and manuscript preparation. Specimens will be processed and stored at the University of Nairobi Pediatric Research Laboratory.

Population Justification: This study will be conducted in Kenyan children and adolescents age 6 weeks-18 years. HIV-exposed uninfected (HEU) populations are growing in Kenya, and there is need to understand health differences and the effect of maternal HIV status and treatment on long term outcomes.

b. Summary table

	Aim 1	Aim 2	Aim 3
Study design	Longitudinal cohort study	Cross-sectional assessments	Implementation surveys, stakeholder workshop
N	Aim 1: 2000 mother-infant pairs: 1000 HEU and 1000 HUU	Aim 2: 4800 children and adolescents and their caregivers	Aim 3: 25-50 HCW, policy makers, stakeholders in pediatric health
Intervention	None	None	None

Outcomes	Neurodevelopment assessment scores, hearing, growth, hospitalization, morbidity and mortality	Neurodevelopment assessment scores, mental health, hearing	Cost, feasibility of screening, referral options for HEU
Enrollment age range	Infants age 6 weeks	3-18 years	>18 years
Health status	HEU, HUU infants	HEU, HUU children and adolescents	NA
Clinical Site	Nairobi, Western Kenya	Multiple sites in the country	NA
Study follow-up	6 weeks to age 4	NA	NA
Specimens	Dried blood spot	Dried blood spot	NA
Specimen collection timeline	Enrollment, yearly	Enrollment	NA
Use of specimens	Telomere length	Telomere length	NA

c. Aim 1

i. **Study design**

Longitudinal cohort study

ii. **Study populations**

2000 HEU and HUU infant-mother pairs enrolled at 6 weeks of age

iii. **Recruitment procedures**

Recruitment of participants

1000 mothers living with HIV (MLHIV) and 1000 HIV-uninfected mothers will be recruited with their infants (HEU and HUU) at 6 weeks during routine postnatal care at 5 MCH clinics (2 in Nairobi, 3 in Western Kenya). Clinic staff will be aware of the study and asked to identify potentially eligible mother-infant pairs and refer them to study nurse. A standard recruitment script will be used for recruitment. A recruitment log will be used to document reasons for declining to participate.

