6. Interested mothers give informed consent to participate
7. Study staff conduct HIV testing for mothers if HIV status not available in mother-baby maternal and child health booklet
8. Study staff collect contact and locator information
9. Study staff collect enrollment data - demographics, HIV status, pregnancy history, ART use and history
10. Study staff conduct anthropometric measures, neurodevelopmental and mental assessments, hearing tests on infant and collect DBS
11. Study staff reimburse client and give appointment for the next visit

v. Laboratory methods

Blood samples: Dried blood spots (DBS) for assessment of telomere length will be collected at enrollment and 12 monthly either using finger prick or venous blood draw (0.5ml).

vi. Data collection instruments

Socio-demographic, pregnancy and post-partum data: Socio-demographic information, family characteristics, medical history (including HIV status), mental health history and substance use history will be collected from caregivers. We will assess for caregiver depression at every visit using PHQ-9.

Growth assessments: Standard anthropometric measures including weight, height/length, head circumference and mid-upper arm circumference will be assessed by trained study staff. These measures will be converted to standard Z-scores using the WHO growth standards.

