Child or adolescent age 3-18 years

Child/adolescent is healthy and HIV negative

Mother HIV status known

Mother HIV diagnosis and ART timing known (for HEU)

Caregiver \geq 18 years willing to take children to clinic for evaluation

iv. Enrollment and study procedures

Enrollment will be conducted at a neutral location (typically public MCH clinic) or at home. No additional visits will be conducted after enrollment.

Determination of HIV status for HEU and HUU: A combination of medical records and HIV testing will be used to determine HIV status of mothers and children. Maternal HIV-positive status during the pregnancy with each child will be determined first using the mother-baby maternal and child health booklet; in the event that this

HOPE study protocol

Version 1.3

July 21, 2020

booklet is not available, records from the HIV care clinic documenting the date when the mother was diagnosed with HIV or started ART will be used (only for HIV positive mothers). In the event of no records are available, maternal report of being diagnosed with HIV either during or prior to the pregnancy with each child will be used (only for HIV positive mothers). For mothers who report not being HIV positive at the time of pregnancy and for whom mother-baby maternal and child health booklets are not available, we will offer maternal HIV testing; mothers who do not consent to HIV testing will not be enrolled.

For HEU dyads, children's HIV negative status will be determined using the same set of procedures (first reviewing mother-baby maternal and child health booklet, then infant HIV testing history records); if the child has not been tested for HIV after the cessation of breastfeeding, HIV testing will be offered for the child. Children ages 7-14 years will be asked to provide assent without mention of HIV; children ages 15-18 will be asked to provide assent (or consent for 18 year olds) with explicit mention of HIV testing and will be told that they can choose whether they wish to share their results with their caregivers. If children decline HIV testing, they will not be enrolled in the study.

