Cognitive outcomes. Cognitive assessments will be done using NIH Toolbox. The battery will include the tests Dimensional Change Card Sort Test, Flanker Inhibitory Control and Attention Test, List Sorting Working Memory Test, Pattern Comparison Processing Speed Test, and Picture Sequence Memory Test, which evaluate working memory, attention, processing speed, and other aspects of executive functioning. The NIH Toolbox has been validated for US children and was recently adapted through a rigorous process involving translation and backtranslation for Kenya, including translation to Dholuo and Kiswahili.

The table below summarizes the tools, age-group they are used in, screening time and domains or disorders they test.

Tool	Age-group	Time (minutes)	Types	Domains/Disorder
MDAT	0.6-5	30	Screening	Gross motor, fine motor, language, social
HearScreen TM	3+	5	Screening	Hearing
NIH Toolbox	6-17	25-30	Screening	working memory, attention, processing speed, executive functioning
Strengths and difficulties questionnaire (SDQ)	3-16 & caregivers	10	Screening	Emotional symptoms, conduct problems, hyperactivity/inattention, peer relationship problems
SNAP-IV	6-12	5-10	Screening	ADHD
PHQ-9	>16 & caregivers	3	Screening	Depression
MINI-KID	6-17	10	Diagnostic	Common psychiatric conditions
MINI	18	10	Diagnostic	Common psychiatric conditions
School performance	>10	1	NA	National exam results Parental report

vii. Sample size determination & data analysis

Effect size calculations: For comparisons of z-scores in MDAT or NIH-toolkit scores, we will be able to detect differences of 0.13-0.18 assuming a standard deviation of 1.0 or 1.4, 80% power and alpha of 0.05 in Aim 1 cohort (Table 10). In the cross-sectional cohort, 2- to 3-fold differences will be detectable, in diagnoses such as depression and ADHD. To detect smaller differences, more HUU could be enrolled in some age-strata based on pilot feasibility.

R61/R33 Aim 1 cohort	Effect detectable (no attrition)		Effect detectable (20% attrition)	Assumptions
Difference in z-score for MDAT	0.13 (SD=1.0)	1000 HEU:1000 HUU	0.14 (SD=1.0)	Standard deviation = 1.0-1.4 ¹⁰⁵
	0.18 (SD=1.4)		0.20 (SD=1.4)	
Difference in ASD prevalence	2.2%	1000 HEU:1000 HUU	2.5%	HUU ASD 2%
	3.3%	500 DTG: 500 EFZ	3.8%	
Difference in SDQ+ prev.	5.2%	1000 HEU:1000 HUU	5.9%	HUU SDQ+ 20%
	7.5%	500 DTG: 500 EFZ	8.5%	
Difference in hearing loss	1.7%	1000 HEU:1000 HUU	2.0%	HUU 1%
	2.7%	500 DTG: 500 EFZ	3.1%	
Difference in TL	0.18	500 HEU: 500 HUU		SD=1.0

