Pitfalls and alternative strategies: The Aim 1 cohort is designed to be homogeneous – with all HEU having initiated ART either before or during pregnancy and all enrolled contemporaneously at 6 weeks of age, which accommodates secular trends in comparisons with the HUU cohort. HUU will be recruited from the same MCH clinic as HEU, which ensures that mothers reside in the same community, and thus have similar sociodemographic characteristics; this attenuates risk for confounding in comparisons between HEU and HUU. We will not enroll during pregnancy, which will under-ascertain perinatal morbidity and preterm birth. However, we have access to 3 ongoing birth cohorts that are accruing pregnancy-enrolled HEU and HUU. Data from those cohorts complement this study, which is designed to be a population-based multi-site urban/rural cohort.

17. Timeline

Timeline: In the first 6 months we will obtain study approval, recruit and train staff and establish study sites. We anticipate to complete enrollment for the longitudinal cohort in the second half of year 1. Aim 2 pilot will begin in the second half of year 1 and be complete in 10 months. Aim 2 population surveys will begin after the pilot in the second half of year 2. Aim 3 activities will be conducted in year 4-5.

Study Timeline					
	Year 1	Year 2	Year 3	Year 4	Year 5
Study approvals, training	■				
Aim 1 Enroll longitudinal cohort		■			
Follow-up longitudinal cohort		■	■	■	■
Aim 2 Pilot cross-sectional cohort		■	■		
Aim 2 Population based assessments			■	■	
Aim 3 Cost analysis				■	■
Aim 3 Stakeholder meeting					■

18. Human subjects

a) Ethical Approval

We will obtain ethical approval from the University of Washington (UW) Human Subjects Division (IRB) and Kenyatta National Hospital-University of Nairobi (KNH-UoN) Ethics and Research Committee (ERC). There will be minimal risk to the participants taking part in this study. Any changes to the protocol will be submitted to the UW IRB and KNH-UoN ERC.

b) Collaborating sites

The study will be conducted in collaboration with the UW, KNH, and UoN. The study will be reviewed by the KNH ERC and UW IRB and will not be started before approvals are obtained from all two organizational review boards.

c) Informed Consent

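### The EFZ-versus-DTG detectable differences hold only for a near-equal regimen split that nothing secures; the stated adjustment omits ART timing, and Aim 1 eligibility does not enforce the ART exposure that Section 16 claims.

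*Protocol*

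**What the plan says.** **Power.** The effect-size table in Section 12.d.vii gives EFZ-versus-DTG rows for ASD, SDQ+ and hearing loss in the Aim 1 cohort. Each assumes "500 DTG: 500 EFZ", at "80% power and alpha of 0.05 in Aim 1 cohort". The detectable differences are 3.3, 7.5 and 2.7 points, or 3.8, 8.5 and 3.1 under the column "Effect detectable (20% attrition)".

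**Recruitment.** Section 12.c.iii says "1000 mothers living with HIV (MLHIV) and 1000 HIV-uninfected mothers will be recruited with their infants (HEU and HUU) at 6 weeks". It sets no quota, stratum or target by regimen. Section 8 says "In 2019, guidelines for ART changed from EFZ-backbone to DTG-backbone regimens, including during pregnancy". The protocol is dated July 2020, and Section 17 places enrolment after approvals.

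**Adjustment.** Aim 1a asks about ART timing and regimen. Section 12.c.vii and its Table 6 list pre-conception ART and EFZ versus DTG as separate comparisons. The a priori cofactors given for all analyses are sociodemographic factors, birthweight, preterm birth, maternal depression and education, infant sex and LAZ. The later analysis paragraph has a similar, shorter set. Neither contains ART timing.

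**Exposure.** Section 16 describes a homogeneous cohort "with all HEU having initiated ART either before or during pregnancy". The Aim 1 criteria in Section 12.c.iii contain no ART requirement. They exclude mothers of unknown HIV status as judged from the booklet, yet step 7 of the procedures in Section 12.c.iv reads "Study staff conduct HIV testing for mothers if HIV status not available in mother-baby maternal and child health booklet". Aim 2 eligibility (Section 12.d.iii) requires "Mother HIV diagnosis and ART timing known (for HEU)".

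**The concern.** Regimen and timing effects are a stated Aim 1a objective. Three features weaken that comparison.

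- The only allocation shown is the most favourable one. If one regimen is scarce, the study can detect only larger differences than the table says, and a null result could be read as more reassuring than it is.
- When guidelines move from one regimen to another at a given date, a woman's regimen may depend on when she started ART. Without adjustment for timing, a difference that arises from pre-conception versus later ART could appear as a regimen effect.
- If a mother can enter as HEU without antenatal ART, her infant belongs to neither regimen group and to neither side of the timing contrast as Section 16 describes the cohort.

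**Working it through.** **Inputs.** From the effect-size table: 1000 HEU, 80% power, alpha 0.05 (taken as two-sided), and reference rates of 2% (ASD), 20% (SDQ+) and 1% (hearing). The table attaches these rates to HUU, not to either regimen. The EFZ:DTG shares are not in the protocol, so the splits below are assumptions.

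**Formula.** Pooled two-proportion z test without continuity correction:

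power = Φ{(|p2 − p1| − 1.96·s0)/s1}, where s0 = √[p̄(1 − p̄)(1/n1 + 1/n2)], s1 = √[p1(1 − p1)/n1 + p2(1 − p2)/n2], and p̄ is the size-weighted mean rate. The detectable difference is the p2 − p1 that gives 80%.

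**Reproducing the plan.** At 500:500 the solution is 3.32 / 7.53 / 2.67 points, against the stated 3.3 / 7.5 / 2.7. At 400:400 it is 3.84 / 8.48 / 3.13, against 3.8 / 8.5 / 3.1. The arithmetic is correct.

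**Unequal splits.** Because the reference rate belongs to neither regimen, each range runs from reference rate in the DTG arm to reference rate in the EFZ arm (1000 HEU, no attrition):

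| EFZ:DTG (assumed) | ASD | SDQ+ | Hearing |
|---|---|---|---|
| 50:50 | 3.3 | 7.5 | 2.7 |
| 40:60 | 3.3–3.5 | 7.7 | 2.7–2.8 |
| 30:70 | 3.5–3.9 | 8.2–8.3 | 2.8–3.2 |
| 20:80 | 4.0–4.7 | 9.4–9.7 | 3.2–4.0 |
| 10:90 | 5.5–7.2 | 12.6–13.3 | 4.4–6.3 |

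**Power at the stated differences, 20:80.** Worked for ASD, 2% versus 5.3%:

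- Reference in the EFZ arm (n = 200): p̄ = (200×0.02 + 800×0.053)/1000 = 0.0464, s0 = 0.01663, s1 = 0.01268. Then (0.033 − 1.96×0.01663)/0.01268 = 0.03, so power is 51%.
- Reference in the DTG arm (n = 800): p̄ = 0.0266, s0 = 0.01272, s1 = 0.01660. Then (0.033 − 1.96×0.01272)/0.01660 = 0.49, so power is 69%.

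The same steps give 59–63% for SDQ+ and 50–72% for hearing.

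**With 20% attrition (800 HEU), 20:80.** 4.6–5.5 / 10.5–10.9 / 3.7–4.7, against the stated 3.8 / 8.5 / 3.1.

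**Cost of adjusting for timing.** If timing explained 20–30% of the variance of regimen (an assumption), the effective size at 500:500 would be about 500×(1 − 0.2) = 400 to 500×(1 − 0.3) = 350 per arm.

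**Adjustment text.** Apart from the two stated sets, a variable can enter a model only through a univariate screen at p < 0.05 on association with growth. That is not the outcome in the MDAT, ASD, SDQ or hearing models. ART use and history are collected at enrolment (Section 12.c.iv, step 9), so timing is available.

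**Eligibility text side by side.** The exclusion list removes mothers whose status is unknown from the booklet, and eligibility is assessed at step 4. Section 12.c.iv nevertheless offers HIV testing to untested mothers, and step 7 tests those with no booklet status after consent. On the first reading such a mother never enters. On the second, a mother first found positive at about six weeks, with an HIV-negative infant, meets every written criterion. On neither reading does a criterion require ART before delivery, as Section 16 asserts.

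**The case against.** - *The table prints its assumption openly, and no regimen shares are known.* Both are true. A reader might infer that the stated differences are wrong, or that a heavy imbalance is established. The protocol supports neither. A 2019 guideline change does not fix the regimen mix at enrolment, Section 9 speaks of DTG use as still expanding, and 40:60 would cost almost nothing. What remains is that the single case shown is essentially the most favourable one.
- *The loss depends on where the reference rate sits.* This is also true, and quoting only the EFZ-arm figures would overstate it. At 20:80, power is below 80% for all three outcomes under either placement.
- *Mutual adjustment of two named exposures is SAP detail, and the cofactor list is introduced as including certain items.* This has some force, since the list is not declared closed. But the protocol states adjustment sets twice without ART timing, and the one other route into a model is tied to growth. That regimen actually is confounded with timing would be too strong a claim: it may be.
- *The booklet exclusion may already keep untested mothers out, and few are likely.* This is possible. The exclusion and the testing step contradict each other, so it cannot be said that such mothers will enter, only that the text does not settle it.
- *Aim 2 might be read as requiring documented ART before delivery.* It does not. It asks that diagnosis and ART timing be known, and where records are missing it accepts the mother's report of when she was diagnosed.

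**Conclusion.** The point stands in limited form. The EFZ-versus-DTG figures are arithmetically right but conditional on a near-equal split of all 1000 HEU mothers that no recruitment rule secures. If the EFZ share were 20%, the detectable differences would be 4.0–4.7 / 9.4–9.7 / 3.2–4.0 points rather than 3.3 / 7.5 / 2.7. The size of any loss rests wholly on assumed shares and on which regimen carries the reference rate. The regimen contrast may be confounded with ART timing, because the stated adjustment sets leave timing out; the documents give no figure for the size of that bias. The Section 16 statement on ART exposure is not backed by the Aim 1 criteria, and the handling of mothers without a booklet HIV status is contradictory. None of this bears on the power figures for HEU versus HUU.

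**What to change.** 1. In the effect-size table, label 500:500 as the best case. Add detectable differences for a range of EFZ:DTG splits, with the reference rate placed in each arm in turn. Cost: restated rows only.
2. State that EFZ versus DTG will be adjusted for ART timing (pre-conception versus in pregnancy), with enrolment date added in a sensitivity analysis. Cost: no new data, but some loss of precision if regimen and timing are correlated.
3. Reconcile the Aim 1 eligibility criteria (Section 12.c.iii), the testing text (Section 12.c.iv, including step 7) and Section 16. One way is to require, as Aim 2 does, that maternal HIV diagnosis and ART timing be known for Aim 1 HEU, and to analyse mothers without antenatal ART separately from the regimen and timing contrasts. The other is to drop the statement that all HEU mothers had ART before delivery. Cost: a line or two of text; under the first option, probably few mothers are affected, though the protocol gives no number.

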involved in recognizing mental health outcomes that may take 1-2 decades to be detected complicates investigations further. As ART regimens evolve, monitoring for HEU outcomes will remain important. Maternal HIV prevalence is >20-30% in some regions of sub Saharan Africa, which means that a substantial proportion of *all* children/adolescents have fetal exposure to HIV/ART, which may have long-term impact on developmental outcomes. Ideally, well conducted studies could provide reassuring data of limited risks from fetal HIV/ART exposure. Detecting epidemiologic signals for links between fetal HIV/ART exposure and mental health outcomes is important to inform our understanding of biologic or psychosocial determinants of adolescent mental health both among HEU and in general. If there are risks, regimens and psychosocial interventions could be tailored to decrease these risks as mechanisms are better understood and children at risk could be identified for early intervention.

[figure not shown]
9. Literature review

Parallel longitudinal cohorts and population-based cross-sectional groups combined in a virtual cohort will provide an innovative and efficient approach to evaluate HEU from infancy to adolescence, assessing short- and long-term outcomes. Our proposed cohorts span urban and rural settings and span HEU/HUU from 6 weeks to 18 years with adequately powered age strata to discern differences in mental health outcomes. This deep and broad assessment is novel and will provide distinct cohorts in which to demonstrate epidemiologic consistency in findings regarding HEU risk and cofactors. Parallel study designs provide complementary strengths – the longitudinal infant cohort with universal Option B+ coverage and homogeneous age at recruitment provides clear ascertainment of perinatal HIV/ART exposure and early outcomes with minimal bias; this cohort will provide timely data as DTG use expands and could be extended past the study period. The older cross-sectional cohort may reveal associations of fetal HIV/ART exposure with mental health outcomes that are not detectable in early childhood. Multiple cohorts strengthen causal inference – by including longitudinal and population-based surveys, short- and long-term outcomes, and nested case-control studies – we can strengthen causal inference by demonstrating *consistency* between studies.

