This study will provide rigorous epidemiologic evidence regarding the influence of fetal exposure to HIV and ART on developmental and mental health outcomes from infancy to adolescence, including obtaining a national population-based estimate of HEU burden of developmental and mental health outcomes and strategies for programmatic surveillance and referral.

11. Specific aims and hypotheses

Aim 1: Within a longitudinal cohort of 1000 HEU and 1000 HUU infants enrolled at 6 weeks of age from 5 MCH clinics and followed 6-monthly:

HOPE study protocol

Version 1.3

July 21, 2020

Aim 1a. To compare HEU and HUU infants and children for growth, hearing, and neurodevelopmental outcomes; and determine influence of ART timing/regimen on HEU outcomes. To determine whether fetal HIV/ART exposure impacts 4-year neurodevelopmental outcomes; and assess impact of peripartum ART regimen and timing.

Aim 1b: To compare telomere length in HEU and HUU and determine associations with neurodevelopmental outcomes.

Aim 2a: To determine the impact of HEU and HUU status, as well as maternal peripartum ART, on neurodevelopment and mental health (ASD, ADHD, depression, and anxiety). We will pilot a mobile screening strategy to detect adverse neurodevelopmental and mental health outcomes in HEU for use in large-scale screening in Aim 2b. Mothers attending HIV care will be invited to bring their HEU (aged 3-18) (200 HEU, 50 per age-stratum: 3-6, 7-10, 11-14, 15-18) for screening; age- matched HUU will be recruited from the community.

Aim 2b. To estimate population-burden and cofactors of adverse neurodevelopmental and mental health outcomes in HEU using mobile teams to screen HEU in ~100 large HIV Care Clinics throughout Kenya (4000 HEU; age-stratified, 3-6, 7-10, 11-14, 15-18) and 400 age-stratum matched community HUU.

Aim 3. To estimate the cost of this screening strategy and convene stakeholders to review data regarding programmatic integration of HEU screening.

12. Study design and methodology

a. Study area description

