R33 Aim 2				
Difference in BENC1 scores	0.29	1000 HEU: 100 HUU age stratum (7-11yo)		SD=1.0
Difference in ADHD prev.	7.7%	1000 HEU: 100 HUU		2.7% in HUU ¹⁷⁵
Difference in depression prev	10.1%	1000 HEU: 100 HUU per age stratum		HUU 10%

Analyses: For binary outcomes such as ADHD and depression, multivariate generalized linear models (GLM) with log link and binomial family for relative risk estimation clustered by site will be used. For continuous variables such as NIH-Toolkit, we will use multivariate GLM with Gaussian family and identity link. As previously noted in Aim 1, we will include *a priori* potential confounders - maternal depression, preterm birth, and infant birthweight - in multivariate analysis, after assessment of collinearity.

MDAT (social, fine motor, gross motor, language)	GLM
Hearing	GLM
BENCI (processing speed, visual-motor coordination, attention, language, memory, executive function)	GLM
SDQ total domain score	GLM
ADHD screen (analyze positive SNAP-IV and subset validated on MINI-Kid)	GLM
PHQ-9 (prevalence of moderate-severe symptoms)	GLM
Neuropsychiatric diagnoses	GLM

Training procedures for aim 1 and 2

The study team will develop protocols and training materials for clinic staff. A 5-day training workshop will be designed. The package will include the basics of early childhood development, pediatric mental health, screening and use of the study screening and diagnostic tools. The training will cover neurodevelopmental assessments, psychometric testing, and administration, scoring and interpretation of the MDAT and NIH Toolbox. The 5-day nurse training workshop will cover general sensitization to the testing situation, including ensuring that the child follows the instructions, methods of cross-checking to determine whether a child understood instructions, learning when to give breaks, how to re-engage the child and how to react to distress. The training will cover how to recognize need for referrals and provide motivational interviewing and culturally sensitive assessment skills. To ensure quality control, the study coordinator will conduct refresher training for staff to ensure operating procedures are followed consistently. We will also develop checklists for tests requiring multiple tests as well as the use of tablet based tests to ensure quality assessments.

e. Aim 3

i. **Study design**

This Aim of the study involves 2 cross-sectional components:

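### Aim 2 within-HEU contrasts by maternal ART are planned over ages 3-18 with confounder lists that omit child age and birth year, so age or era differences could be reported as ART effects

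*Protocol*

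**What the plan says.** Section 11 gives Aim 2a as "To determine the impact of HEU and HUU status, as well as maternal peripartum ART, on neurodevelopment and mental health". Section 12.d requires the timing of maternal ART to be known for HEU and abstracts records to document fetal ART exposure, so an ART comparison is clearly intended. The population phase samples "4000 HEU; age-stratified, 3-6, 7-10, 11-14, 15-18", with "400 age-stratum matched community HUU" as comparators. Each child is seen once.

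The Background (Section 8) links regimen to time: "In 2019, guidelines for ART changed from EFZ-backbone to DTG-backbone regimens, including during pregnancy". It also remarks that growth may be "less compromised among those who receive Option B+ vs. earlier or no PMTCT regimens". Section 17 adds "Aim 2 population surveys will begin after the pilot in the second half of year 2".

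Section 12.d.vii specifies generalized linear models, clustered by site for binary outcomes, and refers back to Aim 1 for adjustment: "we will include *a priori* potential confounders - maternal depression, preterm birth, and infant birthweight - in multivariate analysis", after a check for collinearity. The Aim 1 list in Section 12.c.vii, stated to apply to every analysis, adds household sociodemographic factors, infant sex, maternal education and length-for-age z-score. It keeps only non-collinear variables associated with growth at p < 0.05. Child age, age stratum and birth year appear in neither list.

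**The concern.** The adjustment lists suit Aim 1, where all infants enrol at about 6 weeks and Section 16 credits contemporaneous enrolment with dealing with secular trends. Nothing equivalent is said for Aim 2, which spans ages 3 to 18.

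Among HEU, children of mothers on older regimens or no ART will tend to be older, and those with more recent regimens younger. If an outcome also changes with age, a contrast that ignores age picks up that change. Length-for-age z-score does not stand in for age, because it is already standardised for age.

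The outcomes most open to this span many ages: SDQ (3-16), hearing (3 and over), MINI-KID and MINI diagnoses (6-18), and Toolbox scores (6-17) if they are not age-normed. Section 9 presents the older cohort as a source of new evidence ("The older cross-sectional cohort may reveal associations of fetal HIV/ART exposure with mental health outcomes that are not detectable in early childhood"), and Section 12.e takes results on at-risk HEU subgroups to policy makers. An age gradient presented there as an ART effect would be a substantive error.

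**Working it through.** **The plan's own figure.** Section 12.d.vii sizes no ART contrast in Aim 2. The nearest entry is a detectable difference of 0.29 SD for 1000 HEU and 100 HUU in one stratum. With two-sided alpha 0.05 and 80% power (stated for Aim 1, assumed here) and SD 1.0: (1.96 + 0.84) × √(1/100 + 1/1000) = 2.80 × 0.105 = 0.294. It reproduces, but it concerns HEU against HUU.

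**Illustration with a true ART effect of zero.** From the protocol: four age strata, 1000 HEU in each, SDQ used through age 16. Assumed: half of the oldest stratum (500) is eligible for SDQ; the share with no maternal ART is 5, 20, 50 and 80% from youngest to oldest; SDQ-positive prevalence depends on stratum only. The one SDQ prevalence in the protocol is 20% in HUU, in the Aim 1 sample-size table.

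Group sizes:
- No ART: 50 + 200 + 500 + 400 = 1150
- ART: 950 + 800 + 500 + 100 = 2350

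*Scenario A, prevalence 15, 18, 21, 24%*
- No ART: 7.5 + 36 + 105 + 96 = 244.5, and 244.5/1150 = 21.26%
- ART: 142.5 + 144 + 105 + 24 = 415.5, and 415.5/2350 = 17.68%
- RR = 21.26/17.68 = 1.20
- Pooled p = 660/3500 = 0.1886; SE = √[0.1886 × 0.8114 × (1/1150 + 1/2350)] = 0.0141; z = 0.0358/0.0141 = 2.54

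*Scenario B, prevalence 18, 19, 20, 21%*
- No ART: 9 + 38 + 100 + 84 = 231, and 231/1150 = 20.09%
- ART: 171 + 152 + 100 + 21 = 444, and 444/2350 = 18.89%
- RR = 1.06; pooled p = 675/3500 = 0.1929; SE = 0.0142; z = 0.0119/0.0142 = 0.84

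Within each stratum the difference is zero, but only because prevalence was held constant inside the stratum. These z values ignore site clustering and the listed covariates.

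**What adding age does.** A simulation used 4000 HEU spread evenly over ages 3-18, no true ART effect, ART exposure falling with age (correlation -0.41 to -0.81), and 300 runs per setting. These inputs are also assumed.

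| Prevalence, age 3 to 18 | Spurious RR, ART v none, age omitted | False positives, age omitted | False positives, age included |
|---|---|---|---|
| 8% to 12% | 0.81-0.90 | 17-52% | 6-7% |
| 5% to 15% | 0.57-0.76 | 77-100% | 4-8% |
| 3% to 20% | 0.37-0.63 | 99-100% | 5% |

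Including age inflates the variance of the ART estimate by 1.2 to 2.9, that is, intervals wider by a factor of √1.2 = 1.1 to √2.9 = 1.7. The steeper rows show how strongly the bias depends on the assumed gradient; they do not estimate it for this study.

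**The case against.** The strongest reply is that no passage states an ART contrast pooled over ages 3-18. Sampling is by age stratum, Section 9 speaks of powered age strata, Section 12.d.vii gives detectable effects per stratum, and a SAP that is not shown may specify more. This stands in part: the bias is a risk under the stated covariates, not a certainty. But the per-stratum sizes concern HEU against HUU, no stratified or age-adjusted ART analysis is stated, and the protocol itself fixes the confounder lists. This is therefore more than detail left to a SAP.

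The era premise is also partly inferred. Only the 2019 switch is dated, the Option B+ remark comes from growth literature, and no ART-by-age distribution is given. That limits what can be said about size, not direction of reasoning.

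Four stronger readings are tempting and not supported:
- *That Aim 2 cannot address DTG at all.* Section 17 gives relative years and no start date, so the oldest age of a DTG-exposed child at survey cannot be derived. EFZ against DTG is planned and sized in Aim 1 only.
- *That the mix of tests biases results generally.* Section 12.d.vii lists a model for each outcome, and SNAP-IV (6-12), PHQ-9 (over 16) and MDAT (about 3-5 in Aim 2) cover narrow ages.
- *That HEU against HUU is materially affected.* HUU are matched by age stratum.
- *That consistency with Aim 1 would be an artefact.* Section 9 claims consistency for HEU risk and cofactors broadly, not for ART contrasts in particular.

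**Conclusion.** The point holds for ART contrasts within HEU in Aim 2, chiefly for SDQ, hearing, MINI-KID and MINI diagnoses, and Toolbox scores if not age-normed. Run over a wide age range with the listed covariates, such a contrast could report age or era differences as ART effects.

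The documents do not allow the size to be determined. In the two worked SDQ scenarios the spurious RR runs from about 1.06, which would pass unnoticed, to 1.20, which would look significant. Both rest on assumed ART shares and prevalences. The conclusion depends on ART exposure varying with birth year, which the Background supports, and on the outcome varying with age or birth era, which is assumed.

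**What to change.** In Section 12.d.vii:

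1. Force child age (continuous or flexible) or age stratum into every Aim 2 within-HEU ART model. Exempt it from the collinearity check and the growth-association screen of Section 12.c.vii, because age is expected to correlate with ART exposure and could otherwise be dropped.
2. Estimate ART contrasts within age strata where the exposure groups overlap, and pool only those estimates. Age can still vary with exposure inside a four-year stratum, so keep continuous age in these models where numbers allow.
3. Tabulate ART exposure by age, and state that contrasts without overlap cannot be separated from birth era. Adjustment cannot recover an effect where nearly all children of an age share one exposure.

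This changes analysis wording only, since age is already recorded for eligibility and stratification. The cost is wider intervals for ART contrasts, and some contrasts may prove barely estimable, which reflects the information actually present.
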